Appendix 4. CTCAE Grade for Laboratory Parameters

CTCAE v4.03	CTCAE Grade				
Adverse Event	1	2	3	4	5
Anemia	Hemoglobin (Hgb) <LLN - 10.0 g/dL; <LLN - 6.2 mmol/L; <LLN - 100 g/L	Hgb <10.0 - 8.0 g/dL; <6.2 - 4.9 mmol/L; <100 - 80g/L	Hgb <8.0 g/dL; <4.9 mmol/L; <80 g/L; transfusion indicated	Life-threatening consequences; urgent intervention indicated	Death
Hypoalbuminemia	<LLN - 3 g/dL; <LLN - 30 g/L	<3 - 2 g/dL; <30 - 20 g/L	<2 g/dL; <20 g/L	Life-threatening consequences; urgent intervention indicated	Death
Alkaline phosphatase increased	>ULN - 2.5 x ULN	>2.5 - 5.0 x ULN	>5.0 - 20.0 x ULN	>20.0 x ULN	-
Alanine aminotransferase (ALT) increased	>ULN - 3.0 x ULN	>3.0 - 5.0 x ULN	>5.0 - 20.0 x ULN	>20.0 x ULN	-
Activated partial thromboplastin time (APTT) prolonged	>ULN - 1.5 x ULN	>1.5 - 2.5 x ULN	>2.5 x ULN; hemorrhage	-	-
Aspartate aminotransferase (AST) increased	>ULN - 3.0 x ULN	>3.0 - 5.0 x ULN	>5.0 - 20.0 x ULN	>20.0 x ULN	-
Blood bilirubin increased	>ULN - 1.5 x ULN	>1.5 - 3.0 x ULN	>3.0 - 10.0 x ULN	>10.0 x ULN	-
Hypercalcemia	Corrected serum calcium of >ULN - 11.5 mg/dL; >ULN - 2.9mmol/L; Ionized calcium >ULN- 1.5 mmol/L	Corrected serum calcium of >11.5 - 12.5 mg/dL; >2.9 - 3.1 mmol/L; Ionized calcium >1.5 -1.6 mmol/L; symptomatic	Corrected serum calcium of >12.5 - 13.5 mg/dL; >3.1 - 3.4 mmol/L; Ionized calcium >1.6 - 1.8 mmol/L; hospitalization indicated	Corrected serum calcium of >13.5 mg/dL; >3.4 mmol/L; Ionized calcium >1.8 mmol/L; life-threatening consequences	Death
Hypocalcemia	Corrected serum calcium of <LLN - 8.0 mg/dL; <LLN - 2.0 mmol/L; Ionized calcium <LLN - 1.0 mmol/L	Corrected serum calcium of <8.0 - 7.0 mg/dL; <2.0 - 1.75 mmol/L; Ionized calcium <1.0 - 0.9 mmol/L; symptomatic	Corrected serum calcium of <7.0 - 6.0 mg/dL; <1.75 - 1.5 mmol/L; Ionized calcium <0.9 - 0.8 mmol/L; hospitalization indicated	Corrected serum calcium of <6.0 mg/dL; <1.5 mmol/L; Ionized calcium <0.8 mmol/L; life-threatening consequences	Death

CTCAE v4.03		CTCAE Grade				
Adverse Event		1	2	3	4	5
Chronic kidney disease	eGFR (estimated Glomerular Filtration Rate) or CrCl (creatinine clearance) <LLN - 60 ml/min/1.73 m ² or proteinuria 2+ present; urine protein/creatinine >0.5	eGFR or CrCl 59 – 30 ml/min/1.73 m ²	eGFR or CrCl 29 – 15 ml/min/1.73 m ²	eGFR or CrCl <15 ml/min/1.73 m ² ; dialysis or renal transplant indicated		Death
Creatinine increased	>1 - 1.5 x baseline; >ULN - 1.5 x ULN	>1.5 - 3.0 x baseline; >1.5 - 3.0 x ULN	>3.0 baseline; >3.0 - 6.0 x ULN	>6.0 x ULN		-
Gamma-glutamyl transferase (GGT) increased	>ULN - 2.5 x ULN	>2.5 - 5.0 x ULN	>5.0 - 20.0 x ULN	>20.0 x ULN		-
Hyperglycemia	Fasting glucose value >ULN - 160 mg/dL; Fasting glucose value >ULN - 8.9 mmol/L	Fasting glucose value >160 - 250 mg/dL; Fasting glucose value >8.9 - 13.9 mmol/L	>250 - 500 mg/dL; >13.9 - 27.8 mmol/L; hospitalization indicated	>500 mg/dL; >27.8 mmol/L; lifethreatening consequences		Death
Hypoglycemia	<LLN - 55 mg/dL; <LLN - 3.0 mmol/L	<55 - 40 mg/dL; <3.0 - 2.2 mmol/L	<40 - 30 mg/dL; <2.2 - 1.7 mmol/L	<30 mg/dL; <1.7 mmol/L; lifethreatening consequences; seizures		Death
Hemoglobin increased	Increase in >0 - 2 gm/dL above ULN or above baseline if baseline is above ULN	Increase in >2 - 4 gm/dL above ULN or above baseline if baseline is above ULN	Increase in >4 gm/dL above ULN or above baseline if baseline is above ULN		-	-
International normalized ratio (INR) increased	>1 - 1.5 x ULN; >1 - 1.5 times above baseline if on anticoagulation	>1.5 - 2.5 x ULN; >1.5 - 2.5 times above baseline if on anticoagulation	>2.5 x ULN; >2.5 times above baseline if on anticoagulation		-	-
Hyperkalemia	>ULN - 5.5 mmol/L	>5.5 - 6.0 mmol/L	>6.0 - 7.0 mmol/L; hospitalization indicated	>7.0 mmol/L; life-threatening consequences		Death
Hypokalemia	<LLN - 3.0 mmol/L	<LLN - 3.0 mmol/L; symptomatic; intervention Indicated	<3.0 - 2.5 mmol/L; hospitalization indicated	<2.5 mmol/L; life-threatening consequences		Death
Lymphocyte count decreased	<LLN - 800/mm ³ ; <LLN - 0.8 x 10 ⁹ /L	<800 - 500/mm ³ ; <0.8 - 0.5 x 10 ⁹ /L	<500 - 200/mm ³ ; <0.5 - 0.2 x 10 ⁹ /L	<200/mm ³ ; <0.2 x 10 ⁹ /L		-

CTCAE v4.03	CTCAE Grade				
Adverse Event	1	2	3	4	5
Lymphocyte count increased	-	>4000/mm ³ - 20,000/mm ³	>20,000/mm ³	-	-
Hypermagnesemia	>ULN - 3.0 mg/dL; >ULN - 1.23 mmol/L	-	>3.0 - 8.0 mg/dL; >1.23 - 3.30 mmol/L	>8.0 mg/dL; >3.30 mmol/L; lifethreatening consequences	Death
Hypomagnesemia	<LLN - 1.2 mg/dL; <LLN - 0.5 mmol/L	<1.2 - 0.9 mg/dL; <0.5 - 0.4 mmol/L	<0.9 - 0.7 mg/dL; <0.4 - 0.3 mmol/L	<0.7 mg/dL; <0.3 mmol/L; lifethreatening consequences	Death
Neutrophil count decreased	<LLN - 1500/mm ³ ; <LLN - 1.5 x 10 ⁹ /L	<1500 - 1000/mm ³ ; <1.5 - 1.0 x 10 ⁹ /L	<1000 - 500/mm ³ ; <1.0 - 0.5 x 10 ⁹ /L	<500/mm ³ ; <0.5 x 10 ⁹ /L	-
Hypophosphatemia	<LLN - 2.5 mg/dL; <LLN - 0.8 mmol/L	<2.5 - 2.0 mg/dL; <0.8 - 0.6 mmol/L	<2.0 - 1.0 mg/dL; <0.6 - 0.3 mmol/L	<1.0 mg/dL; <0.3 mmol/L; lifethreatening consequences	Death
Platelet count decreased	<LLN - 75,000/mm ³ ; <LLN - 75.0 x 10 ⁹ /L	<75,000 - 50,000/mm ³ ; <75.0 - 50.0 x 10 ⁹ /L	<50,000 - 25,000/mm ³ ; <50.0 - 25.0 x 10 ⁹ /L	<25,000/mm ³ ; <25.0 x 10 ⁹ /L	-
Hypernatremia	>ULN - 150 mmol/L	>150 - 155 mmol/L	>155 - 160 mmol/L; hospitalization indicated	>160 mmol/L; life-threatening consequences	Death
Hyponatremia	<LLN - 130 mmol/L	-	<130 - 120 mmol/L	<120 mmol/L; life-threatening consequences	Death
Hyperuricemia	>ULN - 10 mg/dL (0.59 mmol/L) without physiologic consequences	-	>ULN - 10 mg/dL (0.59 mmol/L) with physiologic consequences	>10 mg/dL; >0.59 mmol/L; lifethreatening consequences	Death
White blood cell (WBC) decreased	<LLN - 3000/mm ³ ; <LLN - 3.0 x 10 ⁹ /L	<3000 - 2000/mm ³ ; <3.0 - 2.0 x 10 ⁹ /L	<2000 - 1000/mm ³ ; <2.0 - 1.0 x 10 ⁹ /L	<1000/mm ³ ; <1.0 x 10 ⁹ /L	-
Hypertriglyceridemia	150 mg/dL - 300 mg/dL; 1.71 mmol/L - 3.42 mmol/L	>300 mg/dL - 500 mg/dL; >3.42 mmol/L - 5.7 mmol/L	>500 mg/dL - 1000 mg/dL; >5.7 mmol/L - 11.4 mmol/L	>1000 mg/dL; >11.4 mmol/L; life-threatening consequences	Death
Cholesterol high	>ULN - 300 mg/dL; >ULN - 7.75 mmol/L	>300 - 400 mg/dL; >7.75 - 10.34 mmol/L	>400 - 500 mg/dL; >10.34 - 12.92 mmol/L	>500 mg/dL; >12.92 mmol/L	-

Note: Refer to Common Terminology Criteria for Adverse Events (CTCAE) Version 4.03, which can be found at http://evs.nci.nih.gov/ftp1/CTCAE/CTCAE_4.03_2010-06-14_QuickReference_8.5x11.pdf.

ELECTRONIC SIGNATURES

Signed by	Meaning of Signature	Server Date (yyyy-MM-dd hh:mm)
PPD	Clinical eSigned	2017-07-28 09:22
PPD	Biostatistics eSigned	2017-07-28 17:38

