### **8.6.3. Laboratory Evaluations**

Selected laboratory data will be summarized (n, mean, SD, Median, Q1, Q3, minimum, and maximum) by treatment group and study visit along with the corresponding change from baseline values.

Graded laboratory abnormalities will be defined using the grading scheme in the CTCAE Version 4.03 (refer to [Appendix 4](#)). Grading of laboratory abnormalities for analysis purposes will be performed by the central laboratory.

Incidence of treatment-emergent laboratory abnormalities, defined as values that increase at least 1 toxicity grade from baseline at any time post baseline up to and including the date of last dose of study drugs plus 30 days will be summarized by treatment group. If baseline data are missing, then any graded abnormality (ie, at least a Grade 1) will be considered treatment emergent.

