The CTCAE, Version 4.03 will be used to assign toxicity grades (0 to 4) to laboratory results for analysis. Grade 0 includes all values that do not meet the criteria for an abnormality of at least Grade 1. For laboratory tests with criteria for both increased and decreased levels, analyses for each direction (ie, increased, decreased) will be presented separately.

7.2.2.1. **Treatment-Emergent Laboratory Abnormalities**

Treatment-emergent laboratory abnormalities are defined as values that increase at least 1 toxicity grade from baseline at any postbaseline time point, up to and including the date of last dose of study drug plus 30 days for subjects who permanently discontinued study drug. If the relevant baseline laboratory value is missing, any abnormality of at least Grade 1 observed within the time frame specified above will be considered treatment emergent.

7.2.2.2. **Treatment-Emergent Marked Laboratory Abnormalities**

Treatment-emergent marked laboratory abnormalities are defined as values that increase from baseline by at least 3 toxicity grades at any postbaseline time point, up to and including the date of the last dose of study drug plus 30 days for subjects who permanently discontinued study drug. If the relevant baseline laboratory value is missing, any Grade 3 or 4 values observed within the timeframe specified above will be considered treatment-emergent marked abnormalities.

7.2.2.3. **Summaries of Laboratory Abnormalities**

Laboratory data that are categorical will be summarized using the number and percentage of subjects in the study with the given response at baseline and each scheduled postbaseline visit.

The following summaries (number and percentage of subjects) for treatment-emergent laboratory abnormalities will be provided by lab test and treatment group; subjects will be categorized according to the most severe postbaseline abnormality grade for a given lab test:

- Graded laboratory abnormalities

- Grade 3 or 4 laboratory abnormalities
- Marked laboratory abnormalities

For all summaries of laboratory abnormalities, the denominator is the number of subjects with nonmissing postbaseline values up to 30 days after last dosing date for the laboratory test of interest.

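### Read literally, the Grade 1 creatinine rule counts any rise over a baseline not above ULN as treatment-emergent, flagging roughly 25–83% of subjects in every arm with no drug effect

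*SAP*

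**What the plan says.** SAP 7.2.2 adopts the CTCAE scale for laboratory data: "The CTCAE, Version 4.03 will be used to assign toxicity grades (0 to 4) to laboratory results for analysis". It adds that "Grade 0 includes all values that do not meet the criteria for an abnormality of at least Grade 1".

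Appendix 4 gives two limbs for increased creatinine. Grade 1 is ">1 - 1.5 x baseline; >ULN - 1.5 x ULN" and Grade 2 is ">1.5 - 3.0 x baseline; >1.5 - 3.0 x ULN". The baseline limb of Grade 1 has no minimum rise and no condition attached. Two other rows of the table use baseline, and both restrict it. INR uses ">1 - 1.5 times above baseline if on anticoagulation", and increased hemoglobin uses baseline only when baseline is already above ULN.

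SAP 7.2.2.1 then states: "Treatment-emergent laboratory abnormalities are defined as values that increase at least 1 toxicity grade from baseline at any postbaseline time point". The window closes 30 days after the last dose, and no confirmatory value is required. SAP 7.2.2.3 tabulates these abnormalities by test and treatment group, placing each subject at the worst post-baseline grade. Protocol 8.6.3 says: "Grading of laboratory abnormalities for analysis purposes will be performed by the central laboratory".

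**The concern.** Creatinine varies from draw to draw in a stable subject. A rule that compares several later values with one baseline value, and counts any excess, will flag most subjects by chance. Safety is the primary endpoint, and the graded laboratory table is one of its planned displays. A reader of the creatinine row would see a large share of placebo and active subjects with a treatment-emergent Grade 1 abnormality. A true moderate rise in a minority of treated subjects would add little to that count, because most of those subjects would have been flagged anyway.

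**Working it through.** The plan states no expected rate of creatinine abnormalities, so there is no figure of its own to reproduce.

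**Inputs from the documents**
- Grade 1 and Grade 2 limits: SAP Appendix 4, with the semicolon read as 'or'.
- Baseline: one value, the last on or before the first dose (SAP 3.8.2).
- Chemistry draws after baseline: Weeks 1, 4, 8, 12 and Follow-Up (SAP Appendix 1). Follow-Up is four weeks ± 5 days after the last dose (Protocol 6.4.6), that is day 23 to day 33. The window closes at day 30, so the number of counted draws k is 4 or 5.
- Arms: 50, 50 and 25 subjects (SAP 1.2.1).

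**Step 1: grade at baseline.** A value equal to baseline and not above ULN meets neither limb, so it is Grade 0. Any later value above it is at least Grade 1 (Grade 2 beyond 1.5 × baseline) and so treatment-emergent. A subject with baseline above ULN already holds Grade 1, and a small rise does not count.

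**Step 2: chance of a flag with no drug effect.** If the k + 1 values are exchangeable and untied, baseline is the largest with probability 1/(k + 1), so P(flag) = k/(k + 1), whatever the distribution or SD.
- k = 4: 4/5 = 80%, or 40 of 50 and 20 of 25.
- k = 5: 5/6 = 83.3%, or 41.7 of 50 and 20.8 of 25.

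**Step 3: rounding and serial correlation.** The documents give neither, so both were simulated (200,000 subjects). Assumptions: mean 0.85 mg/dL, between-subject SD 0.17, within-subject CV 3–10%, lag-one correlation 0 or 0.5.

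| Results reported to | Correlation | Four draws | Five draws |
|---|---|---|---|
| Not rounded | 0 | 80% | 83% |
| Not rounded | 0.5 | 77% | 81% |
| 0.01 mg/dL | 0 | 75–78% | 79–82% |
| 0.01 mg/dL | 0.5 | 71–75% | 75–79% |
| 0.1 mg/dL | 0 | 30–63% | 32–67% |
| 0.1 mg/dL | 0.5 | 25–56% | 27–61% |

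Adding a ULN of 1.2 mg/dL lowers these by at most about 2 points.

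**Step 4: other dilutions.** If a share b of subjects has baseline above ULN, the rate is about (1 − b) × k/(k + 1). For b = 10% that is 0.9 × 80% = 72% or 0.9 × 83.3% = 75%. With 10% of visits missing at random it is 78% or 81%.

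**Step 5: what the row can still show.** Suppose 20% of treated subjects have a true rise large enough that all of them are flagged. With k = 4 and no ties the all-grade rate moves from 80% to 0.80 + 0.20 × (1 − 0.80) = 84%, or 42 instead of 40 of 50, beside 20 of 25 on placebo.

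A second simulation (400,000 subjects, same mean and SD) gave 20% of treated subjects a 40% rise. It used five draws, CV 4–8%, ULN 1.20 or 1.25 mg/dL and no serial correlation.

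| Reported to | Rule for Grade 1 | No effect | With effect |
|---|---|---|---|
| 0.01 mg/dL | Literal | 78–81% | 82–84% |
| 0.01 mg/dL | ULN limb only | 1–5% | 13–21% |
| 0.1 mg/dL | Literal | 41–61% | 53–69% |
| 0.1 mg/dL | ULN limb only | 1–4% | 13–18% |

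In the same runs the share reaching Grade 2 or above rose from at most 0.1% to 5–12%.

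**Step 6: noise under the alternative.** Over the wider assumptions of Step 3, with ULN 1.2 mg/dL, a ULN-only Grade 1 flags about 1–8% of subjects with no drug effect.

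**The case against.** The best defence is that the sponsor is applying a recognised scale as the protocol prescribes, that the inflation is the same in every arm, and that renal safety can be read elsewhere. Much of this stands.

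- A reader might infer that the table cannot show a renal signal. The documents do not support that. Subjects are placed at their worst grade, so noise fills only the Grade 1 level, and two-grade rises occur in 0–1% of subjects with no drug effect. Grade 3–4 and marked (three-grade) abnormalities have their own tables. SAP 7.2.1 also summarises and plots creatinine and eGFR numerically, and Appendix 4 has a separate eGFR/creatinine clearance row.
- A reader might infer that a total count of subjects with any graded abnormality is inflated. The visible text plans summaries by laboratory test and specifies no pooled row.
- A reader might infer bias between arms, or inflated adverse event tables. The rule acts equally on all arms, so it masks a difference and does not create one. Protocol 7.1.3 keeps laboratory abnormalities without clinical significance out of the adverse event record.
- A ULN-only Grade 1 has its own blind spot. At an assumed mean of 0.85 and ULN of 1.25 mg/dL, a subject could rise by 47% (1.25/0.85 = 1.47) and stay Grade 0.

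What does not stand is that following CTCAE v4.03 settles the matter. It explains the wording, but it does not make the Grade 1 count informative. Equal inflation is also no answer to the loss of sensitivity shown in Step 5.

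**Conclusion.** The point holds in a limited form. Read literally, the rule flags roughly 25–83% of subjects in each arm with no drug effect. The top of the range (80% for four draws, 83% for five) needs no distributional assumption, but it does need exchangeable values, no ties and few baselines above ULN. A reader might take about 80% as the expected rate. The documents do not give the reporting precision that would justify it, and rounding to 0.1 mg/dL brings the rate down to about 25–67%.

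The damage is confined to the Grade 1 level of the creatinine row. That level is mostly noise and is insensitive to moderate rises in a subset, most clearly at 0.01 mg/dL reporting. A shift in all treated subjects would still show. The conclusion depends on the semicolon meaning 'or', which the SAP does not state. This is a worthwhile, low-cost improvement to a display, and the other renal safety summaries do not depend on it.

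**What to change.** In SAP 7.2.2 and Appendix 4, for the treatment-emergent summary:

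- Assign Grade 1 creatinine on the ULN limb only (above ULN, up to 1.5 × ULN).
- Keep the limb above 1.5 × baseline from Grade 2 upward.
- Add a supplementary row for values above 1 and up to 1.5 × baseline that are not above ULN, so that rises within the normal range are not lost. This row will carry the chance rate shown above and should be labelled accordingly.
- Footnote the departure from the CTCAE v4.03 wording, and list it in SAP 7.7 as a change from Protocol 8.6.3. SAP 7.7 at present declares no deviations.
- Confirm that the central laboratory, which grades for analysis, applies the same rule.

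The cost is a few lines of text, one extra table row, and possibly a small re-derivation of the laboratory's grades. The downside is that Grade 1 creatinine in the main row no longer follows the literal CTCAE v4.03 text. The change affects the analysis display only.
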